## **1. Protocol Statements**

### **1.1. General Information**

This document describes the Hypersensitivity study and provides information regarding procedures for identification and recruitment of participants. The protocol should not be used as an aide-memoir or guide for the assessment and treatment of other patients. Every care was taken in its drafting, but corrections or amendments may be necessary. These will be circulated to the registered investigators in the study. Clinical problems relating to this study should be referred to the Chief Investigator via the Wolfson Centre for Personalised Medicine.

### **1.2. Statement of Compliance**

This study is designed to comply with the guideline developed by the International Conference on Harmonisation (ICH) for Good Clinical Practice (GCP), Research Governance Framework and local NHS Trust and University policies and procedures.

### **1.3. UK registration**

This study will have National Research Ethics Service (NRES) approval, undergo relevant Site Specific Assessment by the relevant Trust Research and Development department and be granted Research and Development Approval from each participating NHS Trust.

Protocol V17 07.02.2023

## 1. Background

Adverse drug reactions (ADRs) are a major cause of patient morbidity and mortality and are also a key reason for drug attrition in drug development ADRs can be classified as 'on target' or 'off target' reactions. On target reactions can be predicted from the known primary or secondary pharmacology of the drug and often represent an exaggeration of the pharmacological effect of the drug. They show simple dose-response relationships and, therefore, can usually be avoided by dose reduction; rarely, they are life-threatening. In contrast, off target reactions cannot be predicted from the known basic pharmacology of the drug, are often dose-independent and can exhibit marked inter-individual variability. They are often referred to as idiosyncratic reactions. Although off-target reactions are less common than on-target reactions, they can be serious and life-threatening.

An epidemiological study conducted in an adult population showed that 6.5% of all hospital admissions were caused by ADRs while 95% of these were 'on target' reactions, 'off target' reactions still remain a clinical problem accounting for 1 in 3000 hospital admissions.

Idiosyncratic "off target" ADRs can be divided into two categories:

- Immune-mediated, where the reaction has either the clinical or laboratory features which suggest that the immune system is involved in the pathogenesis; and
- Non-immune mediated reactions, or "metabolic idiosyncrasy", where non-immune, often poorly characterized pathways are affected by the drug leading to the reaction.

One of the presently accepted mechanisms of drug hypersensitivity is based on the hapten hypothesis. The hapten hypothesis states that low molecular weight compounds must first bind to a macromolecular carrier, such as a protein, in order to become immunogenic. Central to this hypothesis is drug metabolism. Although the physiological role of drug metabolism is detoxification, oxidation of certain drugs can lead to the generation of chemically reactive metabolites and protein haptation. The body responds to the drug-protein conjugate by initiation of an immune response, characterised by either specifically committed T-cells and/or antibodies (produced by B-cells). T-cells play a central role in the regulatory and effector arms of the immune response. T-cell receptors recognise small peptide fragments of the drug protein conjugate that are presented by MHC molecules, after cellular processing. Other studies have shown an alternative pathway of immune recognition, which is independent of drug metabolism and cellular processing. Laboratory studies have detected drug-specific antibodies, T-cells and protein conjugates from hypersensitive and non-hypersensitive individuals.

Protein haptation has been the focus of many immunopharmacological studies. In a recent study by Meng *et al.* it was shown that benzylpenicillin and its re-arrangement product, benzyl penicillenic acid, can form haptens with human serum albumin (HSA); these haptens have been detected in plasma isolated from patients receiving benzylpenicillin therapy. Physiologically relevant synthetic conjugates were prepared and were shown to stimulate T-cells derived from patients that are hypersensitive to benzylpenicillin. Other studies have investigated the haptens formed with flucloxacillin and piperacillin in patients.

Protocol V17 07.02.2023

Hypersensitivity reactions can also occur with chemicals found in commonly used products; due to this, the hypersensitivity project also encompasses any chemical that may cause a person to have an allergic reaction; examples include chemicals contained in hair dyes and fragrances. Therefore, this hypothesis is not exclusively applicable to drugs, but also to chemicals that may cause allergic reactions, for example para-phenylenediamine (ppd) in hair dyes.

In the context of this study, the term chemical is defined as a compound/substance that is either found in a drug or a product.

An improved mechanistic understanding of allergy is crucial as currently available methods to diagnose reactions lack sensitivity and there are no established methods to predict the immunogenicity of a drug. Characterization of drug antigens and definition of the role of protein modification with respect to sensitization is important for the safe development of new drugs and reducing the risk of drug toxicity. An appreciation of quality and intensity of the drug-specific immune response will pave the way for the development of improved diagnostic assays that will increase drug safety by stratification of drug use.

Recently a new group of oncology therapeutics known as checkpoint inhibitors (CPI) and targeted treatments have started to be used in mainstream clinical practice. The toxicities of these drugs appear to characterise a specific subset of 'off-target' hypersensitivity effects leading to the development of a well characterised group of immune-related adverse events (irAEs). These treatments have revolutionised the management of historically poor-prognostic malignancies. However immune related adverse effects (irAE) associated with their use are increasingly concerning, particularly when these drugs are used in combination. The irAEs caused by CPIs mimic endogenous autoimmune disease (AID) in their clinical manifestations and apparent response to treatment. The impact of irAEs will become increasingly significant as their use increases. Thus, understanding of the underlying mechanisms of immune mediated, 'off-target' hypersensitivity is vital. Insight into the immune processes involved in toxicity will inform further research, further drug design, reduce toxicity induced morbidity and optimise patient management and outcomes.

It is clear that the changes that occur at the end-organs targeted by hypersensitivity reactions and the comparison of those changes to the ones seen in blood are essential to complete the picture of hypersensitivity and therefore HYSTs aims and objectives. Thus, the collection and analysis of end-organ tissue, paired with blood samples, will give insight and understanding of what is occurring at the end-organ but also the relationship between systemic and local changes in the presence of hypersensitivity.

## **2. Study Rationale, Objectives and Design**

### **2.1 Rationale**

Drug and chemical hypersensitivity remains a major clinical problem in the UK and USA. Methods for diagnosis of drug hypersensitivity are currently only available for penicillins but not for other drugs. Moreover, current methods for diagnosing penicillin hypersensitivity appear to have low sensitivity and specificity. It is, therefore, important to develop an assay that exhibits high sensitivity and

Protocol V17 07.02.2023

specificity to confidently diagnose drug hypersensitivity. The mechanistic studies described herein may help to identify novel diagnostic reagents for drug hypersensitivity, and provide valuable information that will further our understanding of hypersensitivity reactions with the potential for the development of novel diagnostic assays.

Immune related adverse events (irAE) are having a significant impact on cancer patients who are receiving checkpoint inhibitor (CPI) immunotherapy as part of their oncological treatment. These drugs cause novel toxicities. The constellation of irAEs includes colitis, hepatitis, endocrinopathies, pneumonitis, nephritis and dermatitis. irAEs clinically mimic autoimmune diseases (AID), in which CTLA-4 and PD-1/PDL1 has an established role, and can be severe, permanent and multi-organ effecting. National Cancer Institute Common Terminology Criteria for Adverse Events (CTCAE) Grade 3/4 irAEs are apparently indication-independent and seen in 5-30% (monotherapy) to ~55% (combination therapy) of patients. Insight into the immune processes involved in toxicity will inform further research, further drug design, reduce toxicity induced morbidity and optimise patient management and outcomes.

By nature of their mechanism of action, oncological treatments other than CPIs can also result in profound toxicities. In particular targeted treatments and cytotoxic agents disturb pathways fundamental to epithelial homeostasis, resulting in cutaneous toxicities including but not limited to folliculitis, vitiligo, bullous pemphigoid, non-specific maculopapular rashes and alopecia. Such toxicities can impair patients' quality of life and negatively affect clinical decision-making, which can result in early treatment cessation. Indeed, many of these treatments are increasingly being utilised in conjunction with CPIs supporting the need for better insight into the on and off target effect of these treatments.

## 2.2 Aims and objectives

The aim of this project is to investigate the mechanism(s) of drug-induced and/or chemical-induced hypersensitivity reactions. In order to study the mechanistic aspects of drug/chemical hypersensitivity novel proteomic mass spectrometric-based methods together with cell-based assays will help us to determine the chemical and cellular mechanisms as follows:

- (1) Retrospectively using a number of drug (including but not limited to sulfamethoxazole, carbamazepine, lamotrigine, phenytoin, abacavir) and beta-lactams (including but not limited to penicillins, cephalosporins, carbapenems, monobactams and beta lactamase inhibitors), chemical (including, but not limited to, hair dye [para-phenylenediamine]) and fragrance [including, but not limited to, cinnamic alcohol, eugenol]) allergens as paradigms.
- (2) Prospectively using patients admitted to hospital with any drug induced hypersensitivity.
- (3) Prospective pharmacokinetic study to investigate protein haptening over a stipulated time-frame.
- (4) Use prospectively and retrospectively identified patients to understand the mechanism of oncological treatments including CPIs 'off-target', immune mediated adverse events (irAEs).

The study will define the basic mechanisms of hypersensitivity in terms of drug metabolism, hapten formation, and immunology of both the innate and adaptive immune system (examples include T-cells, B cells, dendritic cells etc) to investigate overall aspects of immune responses to drugs/chemicals.

Protocol V17 07.02.2023

The critical questions to be addressed are:

- What is the interaction between the hapten and the immune system?
- Is there a threshold of hapten formation to trigger immune responses?
- What is the mechanism of cellular presentation of the drug?
- What is the role of immune cells, for example T cells, and their specific phenotype in the immune response?
- Is there potential to use haptened peptides as diagnostic reagents?

The integration of chemical, biochemical and immunological expertise will provide insight into the critical question of how low molecular weight chemicals cause serious tissue injury in man.

With regards to oncological therapies, the hypothesis is that there are identifiable immune parameters that are altered in response to CPIs and targeted treatments resulting in irAEs that can be modelled to determine underlying immunopathological mechanisms. Thus this extends focus within 'What is the role of immune cells, for example T cells, and their specific phenotype in the immune response?' Another critical question is what happens to non-cellular immune mediators in this situation. The main aim of this project is to determine the molecular and cellular parameters affected by CPIs and other oncological treatments in the patient population and those that experience irAE toxicity. We will also investigate the immunophenotypical changes seen in involved end-organs. The project will also establish if there is a dose-toxicity relationship, identify person-specific factors that may predispose/predict susceptibility to irAEs and identify autoantibodies involved in irAEs.

For each drug / chemical, or any drug class, we will aim to recruit a maximum of 100 complete cases.

### **2.3 Study Design**

The following studies will define the basic mechanisms of drug hypersensitivity in terms of drug metabolism and hapten formation, in combination with immunological assays.

- Proteomics investigation into hapten formation in patient plasma.
- Evaluation of the cellular mechanism of hypersensitive reactions induced by drugs and/or chemicals.
- Identification of mRNA profiles in patient cells
- Evaluation of the cellular mechanism of 'off-target' hypersensitivity irAE induced by drugs including oncological immunotherapies using cytometry techniques and cytokine arrays
- Evaluation of the humoral response to drugs including oncological immunotherapy and their role in 'off-target' hypersensitivity irAEs using protein arrays
- Evaluation of end organ tissue markers of hypersensitivity using histopathological, cytological, immunohistochemical and cytometry techniques
- Identification of patient HLA and genomic profiles (including single cell characterisation)

Protocol V17 07.02.2023

The overall study design is outlined in Figure 1.

[figure not shown]

Figure 1: Summary of study design incorporating hypersensitivity to oncological immunotherapy

## 2.4 Patient Identification

There are two separate arms to the clinical protocol, a case-control study and a more limited cohort study

### 2.4.1 Case-Control Study

T-lymphocytes are thought to be involved in the pathogenesis of certain immunological drug reactions, causing tissue damage indirectly through the action of cytokines or directly by the secretion of cytolytic molecules. To stimulate a T-cell response a drug must act as an antigen and in some way ligate specific T-cell receptors. Despite this, the paucity of studies that define drug antigens has severely restricted mechanistic studies that relate the chemistry of antigen formation to immune function. In order to evaluate the relationship between hapten formation and the immune response, lymphocytes (T- and B-cells and other immune cell types) will be isolated from subjects with a history of hypersensitivity along with cells from appropriate non-hypersensitive control patients. Whole blood samples will be collected to:

Protocol V17 07.02.2023

- Characterise drug antigen-specific T-cell and B-cell responses
- Characterise the relative involvement of different T-cell populations
- Measure effector molecules secreted from stimulated T-cells (e.g., cytokines) and B-cells (antibodies)
- Quantify regulatory T-cell expression and activity
- Generate and characterize the phenotype and function of drug antigen specific T-cell clones.
- Generate B-cell lines and dendritic cells for use as antigen presenting cells in functional assays.
- Characterise an overall immunophenotype that occurs in response to therapy with oncological therapies (CPIs, targeted treatments and chemotherapy)
- Characterise the impact of changes to the microbiota on the immune system in the setting of adverse drug reactions
- Transcriptomics, HLA typing and single cell work will also be undertaken

All methods needed to complete the proposed experiments are established and performed routinely.

In addition, whole blood samples from cases and controls that are undergoing drug treatment will be collected and the hapten formed in plasma will be identified and quantified by mass spectrometry methods established in CDSS. This will allow us to evaluate the relationship between hapten formation and drug hypersensitivity.

Finally, in order to investigate and identify genomic factors associated with hypersensitivity reactions to certain drugs, genomic-based experiments are planned that will require the extraction of RNA from cells. Following RNA extraction, microarray and other assays will be performed to evaluate whether there are differences in the transcriptome between subjects with and without ADRs.

#### *2.4.1.1 Case control Study – Drug Class NOS*

##### *Case group*

- Panels of patients that have had hypersensitivity to the paradigm drugs/chemicals will be identified retrospectively through clinic attendances, referrals or existing clinical databases/systems.
- Prospectively patients that are attending hospital with any drug or chemicals induced skin reactions will be recruited locally and/or nationally.

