## **2.4.2 Cohort Studies**

### *2.4.2.1 Cohort Study – Drug Class NOS*

For each drug, and where appropriate, a small cohort of non-allergic control patients that are being administered the drug as part of their normal clinical care will be recruited to investigate the pharmacokinetics of hapten formation and clearance. Blood sampling will be detailed in section 5.

For each drug / chemical, or any drug class, we will aim to recruit no more than ten participants.

Currently, we have no plans to recruit participants under the age of 18 years to the cohort aspect of this study.

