## **4. Selection, Recruitment and Withdrawal of Participants**

### **4.1 Participant Selection**

#### **4.1.1 Case Control study – Drug Class NOS**

##### *Inclusion Criteria for Case-Control Studies (Adult)*

###### *Case (Age $\geq 18$ years):*

- a. Subject is willing to take part
- b. 18 years or over
- c. Diagnosis of drug hypersensitivity as per criteria laid out by the Phenotype Standardization Project. or clinician decision
- d. Written informed consent obtained

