###### *Control groups 1 and 2:*

- a. Participant willing to take part
- b. Currently taking the drug in question without adverse reactions (Control group 1)
- c. Healthy volunteers who may or may not have been exposed to paradigm drugs/ chemicals without ADRs (Control group 2)
  
- d. Ethnically matched to the index patient
- e. Written informed consent obtained

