## 12.2 Appendix 2: Patient Visit Schedule for Drug Class NOS studies

**Visit 1: Patient Recruitment (Identification of patients on active drug treatment either with or without evidence of ADR to drug).**

1. Consent	Written and verbal consent for inclusion into study
2. Blood sampling	Blood sample (up to 500mL) collected into a lithium/heparin / EDTA vacuette
3. Initial assessment	PMH/admission details  Current medications (including herbal and over the counter medications)  Alcohol/smoking/recreational drug use  Height/weight/ethnicity

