## 12.7 Appendix 7: Data to be collected in the CRF

- ❖ Date of Birth
- ❖ Weight (current and, if available, historical values including birth weight)
- ❖ Height (current and, if available, historical values)
- ❖ Past medical history including autoimmune disease
- ❖ Allergies
- ❖ Family history including allergies and autoimmune disease
- ❖ Smoking history (of older participants, and of home environment)
- ❖ Alcohol intake (of older participants)
- ❖ Ethnicity questionnaire
- ❖ Current medications
  - Dose
  - Duration of treatment
- ❖ Medications at time of reaction
  - Dose
  - Duration of treatment
- ❖ Other medications (herbal, over the counter, recreational)
  - Dose
  - Duration of treatment
- ❖ Information regarding drug reaction
  - Dose at time of reaction
  - Duration of treatment
  - If the drug/s was re-challenged
  - Recurrent reactions
  - Ongoing supportive therapy
- ❖ Clinical samples and investigational results
  - Haematological
  - Clinical Chemistry
  - Coagulation
  - Skin patch test
  - Biopsy

[figure not shown]

Protocol V17 07.02.2023

**12.8 Appendix 8:** Flow chart for recruitment via the Yellow Card Reporting System

[figure not shown]

**12.9 Appendix 9:** Flow chart for recruitment via industry partners

Protocol V17 07.02.2023

**12.10 Appendix 10:** Flow chart for recruitment via private healthcare providers

Protocol V17 07.02.2023

12.11 Appendix 11: **Flow chart for prospective cohort study for patients on treatments in oncology**

Procedures	Visit 1	Visit 2 (Up to 4 weeks)
	Informed consent	X
Demographics	X	
Medical history	X	
Punch biopsy (pre or post treatment)	X	X
Observation of treatment		X
40ml blood sample	X	X
DLQI	X	X

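### Hair-dye and fragrance chemicals are in scope, but the case criterion is worded for drugs and no control group for them is required to be exposed and tolerant

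*Protocol*

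**What the plan says.** The Background (section 1) states that "the hypersensitivity project also encompasses any chemical that may cause a person to have an allergic reaction". Objective 1 in section 2.2 lists, beside the drugs, "chemical (including, but not limited to, hair dye [para-phenylenediamine]) and fragrance" allergens as paradigms, and the same section sets a maximum of 100 complete cases per drug or chemical. Section 2.4.1.1 carries this into recruitment: "Panels of patients that have had hypersensitivity to the paradigm drugs/chemicals will be identified retrospectively". It also takes prospective patients whose skin reaction was caused by a drug or a chemical.

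The operative text is worded differently:

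- **Cases (4.1.1).** Adult criterion c reads "Diagnosis of drug hypersensitivity as per criteria laid out by the Phenotype Standardization Project", followed by a short alternative that allows the clinician to decide. Paediatric criterion d has the same form.
- **Control group 1 (4.1.1).** "Currently taking the drug in question without adverse reactions (Control group 1"; section 2.4.1.1 likewise describes this group as being on drug therapy.
- **Control group 2 (2.4.1.1 and 4.1.1).** Healthy volunteers without reactions. Chemicals are mentioned, but exposure is optional.
- **CRF (Appendix 7).** Exposure is recorded as medications with dose and duration, and the event under "Information regarding drug reaction". Allergies and a skin patch test are also listed.
- **Visit 1 (Appendix 2).** The heading is "Identification of patients on active drug treatment either with or without evidence of ADR to drug".

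**The concern.** In a case-control comparison of immune responses, controls need to have had the chance to react. For drugs, Control group 1 secures this: its members take the drug and tolerate it. For chemicals nothing equivalent is required. If the controls for a hair-dye allergen have largely never met it, a T-cell or antibody response that merely marks past contact will separate cases from controls just as a response that marks allergy would.

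The contrast most exposed to this is in section 3.4, where the sensitivity and specificity of novel peptide reagents are judged by comparing allergic people with controls. Section 2.2 asks whether such peptides could serve as diagnostic reagents, so a specificity obtained from unexposed volunteers would bear directly on one of the study's own questions. The case side has a separate weakness: a named paradigm depends on an unclear clause for its patients to be eligible at all.

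**Working it through.** The protocol gives no figure on this point to reproduce. The 100-case maximum is a ceiling with no derivation. The check is a comparison of text, plus one identity.

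**1. Does the word drug already cover hair dye?** The Background defines a chemical as something found in either a drug or a product. That widens chemical to take in drugs; it does not widen drug to take in products. The phenotype-standardisation paper in the reference list is itself titled for drug-induced skin injury. The drug wording in 4.1.1 therefore cannot be read as including chemicals by definition.

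**2. Can a chemical case enter?** There are two readings of the clinician-decision clause.

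- It replaces only the published criteria. The diagnosis is still drug hypersensitivity, and a hair-dye case does not meet it.
- It stands alone. A hair-dye case can enter on the clinician's judgement.

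The text does not settle which is meant.

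**3. Which controls are available for a chemical case?**

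| Group | Exposure required | Open to chemical cases as worded |
|---|---|---|
| Control group 1 | Currently taking the drug | No |
| Control group 2 | None | Yes, exposure unknown |

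Let *e* be the share of Control group 2 members exposed to the chemical. The protocol places no bound on it, so *e* can be anything from 0 to 1.

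**4. Could exposure be sorted out at analysis?** Appendix 7 has allergies and a patch test, which can document allergy in a case. Neither tells us whether a non-allergic volunteer has used the product, and no field for product, chemical, frequency or last use is listed. On the listed data, *e* is not only unfixed but unmeasured.

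**5. Direction of the bias.** Let *t* be the proportion of exposed-tolerant people who test positive and *u* the proportion of unexposed people who do. Then:

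- positive rate among controls = *e·t* + (1 − *e*)·*u*
- apparent specificity = 1 − [*e·t* + (1 − *e*)·*u*]
- specificity in exposed-tolerant people = 1 − *t*
- difference (apparent minus exposed-tolerant) = (1 − *e*)(*t* − *u*)

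The difference is zero if all controls are exposed (*e* = 1) or if exposure alone does not change the response (*t* = *u*). Otherwise, with *t* above *u*, specificity is overstated, and most so at *e* = 0, where the excess is *t* − *u*. The protocol gives no value for *t*, *u* or *e*, so the direction can be stated under that assumption but the size cannot.

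**The case against.** The strongest reply is that the intention is plain and the damage limited. Section 2.4.1.1 expressly recruits chemical cases, the clinician-decision clause offers a way in, and Control group 2 names chemicals, so it may well include tolerant users of common products. Much of the planned work is done within cases: section 3.3 describes T-cell clones, cross-reactivity and cytokine patterns in cells from hypersensitive people, none of which depends on who the controls are. The Visit 1 heading is loose text in an appendix rather than an eligibility criterion; read literally it would also shut out retrospective drug cases who have stopped the drug.

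Most of this stands. It narrows the point to case-versus-control contrasts and makes the Visit 1 heading a matter of tidying. It does not supply a control group that must be exposed and tolerant, nor a field by which such people could be found afterwards. That Control group 2 may contain them is not the same as knowing which members they are.

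A reader might also see a defect in the small cohort of section 2.4.2.1, which says "For each drug / chemical, or any drug class, we will aim to recruit no more than ten participants" although its members are given the drug in normal care. That section opens with a where-appropriate qualifier and ten is a ceiling, so the stray reference to chemicals shows no harm.

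**Conclusion.** The point holds as an inconsistency between scope and operative text, with a real but bounded effect on inference. Chemical cases are not clearly eligible. Their only controls are volunteers of unknown exposure, and the listed data cannot identify the exposed-tolerant ones. Every chemical paradigm is affected, each up to the 100-case maximum, in its case-versus-control immune-response contrasts. The numerical bias cannot be given; its direction rests on the assumption that exposure alone raises the response.

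Stronger conclusions that a reader might draw are not supported:

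- *No chemical case can qualify.* The clinician-decision clause leaves a possible route.
- *The CRF serves drugs only.* It lists allergies and a patch test; what is missing is product or chemical exposure.
- *The plasma hapten comparison is confounded for chemicals.* Section 2.4.1 limits that comparison to people undergoing drug treatment.
- *Objective 1 cannot be answered for chemicals.* The within-case mechanistic work is untouched, and some Control group 2 members may be exposed.

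The drug and oncology arms are not affected. The wording should be corrected, but nothing here undermines the study as a whole.

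**What to change.** 1. In section 4.1.1, reword adult criterion c and paediatric criterion d to cover drug or chemical hypersensitivity.
2. Extend Control group 1, in the adult and paediatric lists and in section 2.4.1.1, to people currently using a product that contains the chemical without a reaction. Alternatively, require known, tolerated exposure for any Control group 2 member used as a control for a chemical.
3. Add to Appendix 7 the product or chemical, its frequency of use and the date of last use, for cases and controls alike.
4. Align the Visit 1 heading in Appendix 2 with these changes.
5. State that, for chemicals, allergic-versus-control comparisons, including the reagent work in section 3.4, use exposed-tolerant controls, with unexposed volunteers reported separately.

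The cost is a protocol wording amendment, a few CRF fields and screening volunteers for product use. No new sampling or procedure is needed.
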